In this study, the main parameter of effectiveness is the proportion of patients with acute respiratory viral infections, including COVID-19, at the end of the period of preventive administration of the drug. The study is planned to show that in the study group, the number of patients with acute respiratory viral infections, including COVID-19, will be significantly less compared to the control group.

The efficiency parameter was selected based on international recommendations for manufacturers of medicines and biological products [28].

The null hypothesis will be tested by comparing the number of cases in the two groups at the end of the period of preventive administration of the drug. It is expected that at least 90% of randomized patients will be suitable for inclusion in the population of the primary analysis (PP). The statistical purpose of the study is a comparative study of the effectiveness of the preventive regimen of the drug. In the main group of study I, study drug Ingaron 100,000 IU, lyophilizate, will be used to prepare a solution for intranasal administration, 1 time a day every other day for 10 days with a repeat of the 10-day course of preventive administration after 7 days of interruption.

To estimate the sample size in this study, an 80% power level was taken (P – probability of not missing the present effect is 0.8) and a one-sided level of statistical significance of 5% (α – the probability of making an erroneous decision about the presence of an effect is less than 0.05). The statistical criteria used are one-sided due to the availability of information about the superiority of the effect of the study drug over the lack of preventive measures against the nosology being studied [28].

Thus, the sample size was calculated based on the following parameters:

- at the required significance level $\alpha = 0.05$, the value of $Z = 1.96$;
- level of statistical power is assumed to be 80%, the value of $Z = 0.84$;
- method of sample formation – randomization using random elements.

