- ❖ All participants included in the study (FAS, Full Analysis Set). This population will be used to describe basic characteristics, including demographic and anthropometric indicators, data on concomitant diseases, and will also be used as the main population to assess performance parameters. In this case, the participant's group will be determined by the "intention to treat" (ITT Analysis).
- ❖ Auxiliary analysis of effectiveness parameters is planned for all subjects who completed the study without significant deviations from the study protocol (PP, Per Protocol).

Methods of descriptive statistics

For numerical indicators, such as demographic and anthropometric data (body weight, age, height, BMI), as well as numerical performance parameters will be calculated:

- Number of missing values (N);
- Minimum value (Min);
- Maximum value (Max);
- Arithmetic Mean (M);
- Standard Deviation (SD);
- 95 % confidence interval (CI) for the mean;

- Median (Me).

For qualitative variables (frequency of AE/SAE development, for example), absolute number in the n/N format will be given, as well as the percentage (%).

Analysis of basic characteristics

The distribution of subjects, demographic and baseline characteristics will be presented using descriptive statistics methods for all subjects included in the study (FAS-population). An intergroup comparison of the basic quantitative characteristics will be carried out using the t-test (or the Mann-Whitney test), depending on the type of data distribution. For categorical data, the χ^2 -criterion or Fisher's exact test will be applied if the expected frequency in any of the cells is less than 5.

Standard methods available in the XLSTAT 2020.3 program will be used for data analysis.

When analyzing numerical data, preliminary testing of variables for the normality of the distribution will be carried out using Shapiro-Wilk's test, as well as a test for asymmetry and kurtosis with an indication of the p value when testing the null hypothesis of the normal distribution of the variable. In the case of a normal distribution, an intra-group comparison of parameter changes is carried out using a paired t-test. For a comparative evaluation, the χ^2 -criterion or the exact Fisher test will be used if the expected frequency in any of the cells is less than 5.

Significance level

A significance level of 0.05 will be used in all tests. Correction for the multiplicity of comparison is not introduced.

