Analysis of the source data

Demographic characteristics, baseline, and follow-up characteristics such as anamnesis, comorbidities and medications used will be described by treatment groups for the ITT population and then safety, if they differ.

⁶ URL <https://www.R-project.org/>

⁷ <https://www.r-project.org/doc/R-FDA.pdf>

Primary Endpoint Analysis

The main parameter of the effectiveness of the preventive use of Ingaron® is the proportion of patients with acute respiratory viral infections, including COVID-19, at the end of the period of preventive administration of the drug (measurement time: 28 days).

In accordance with the purpose and objectives of the study, the null and alternative hypotheses are formulated as follows:

- Null hypothesis (H_0) consists in the assumption that the prophylactic administration of Ingaron will not lead to a change in the incidence of acute respiratory viral infections, including COVID-19, among adult volunteers;
- Alternative hypothesis (H_a) is that in the study group, the proportion of ARVI cases, including COVID-19, will differ from the control group.

$$H_0: \mu_1 = \mu_2$$

$$H_a: \mu_1 \neq \mu_2,$$

where μ is the fraction of the main variable for the corresponding group.

To test these hypotheses, the method of a two-way variant of the Fisher's exact test (with expected frequencies less than 5) or the Pearson's chi-squared test (χ^2) (with the Yates correction for expected frequencies more than 5, but less than 10) will be used.

In all cases, the significance level (α is the probability of an error of the first kind) 0.05 will be used.

The analysis of the primary efficiency parameter will be carried out on the ITT population (main analysis), as well as – additionally – on the PP population (additional analysis).

Data on the case of ARVI (COVID-19) is collected during the entire study by filling out a form on the registration of a case of ARVI.

Secondary Endpoint analysis

The following secondary efficacy parameters in this study are quantitative indicators that will be compared between treatment groups:

- proportion of patients with confirmed COVID-19 at the end of the period of preventive administration of the drug (measurement period: 28 days);
- proportion of patients with acute respiratory viral infections, including COVID-19, at the end of the observation period (change period: 2 months);
- percentage of patients with confirmed COVID-19 at the end of the follow-up period (change period: 2 months);

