5.2. The size of the sample under study

The estimation of the sample size of subjects was based on the following parameters:

- bilateral significance level $\alpha=0.05$ Z value = 1.96;
- statistical power level is 80%, Z-value = 0.84;
- method of sample formation — randomization using elements of randomness;
- statistical criteria used are two-sided due to the lack of a posteriori information about the superiority of the effect of the study drug over the placebo effect.

Calculation results:

- number of volunteers who must complete participation in the study in accordance with the protocol is 286 in the group or a total of 572 participants.
- number of randomized participants is 315 in a group or total 630 people
- number of screened volunteers – up to 642.

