5.5. Populations of participants for analysis

The following populations will be formed for analysis: ITT, PP and safety; additionally: ITT_NV, PP_NV, ITT_NV_BE, PP_NV_BE.

Statistical data analysis will be carried out in the following populations of participants:

1. Population of all included and randomized participants (intention-to-treat, ITT): all randomized participants who were exposed to the study drug, regardless of the degree of protocol compliance during the study. This data set is the main one for the analysis of primary and secondary effectiveness parameters;
2. Population of participants who completed the study according to the protocol (per protocol, PP): all randomized subjects who completed participation in the study in accordance with the protocol (completed the prescribed period of treatment and follow-up without significant deviations from the protocol). This data set is additional for the analysis of primary and secondary effectiveness parameters;
3. Safety population: The data set analyzed for safety assessment is identical to the ITT data set. However, unlike the population depending on the prescribed treatment, participants are analyzed depending on the actual treatment (if it differs from the treatment that was prescribed by randomization). All types of safety analysis will be based on the use of a data set for security assessment;
4. Modified population of all included and randomized participants (intention-to-treat, ITT) not vaccinated against COVID-19: ITT_NV. This data set is additional for the analysis of the primary efficiency parameter;
5. Modified population of participants who completed the study according to the protocol (per protocol, PP), not vaccinated against COVID-19: PP_NV. This data set is additional for the analysis of the primary efficiency parameter;
6. Modified population of all included and randomized participants (intention-to-treat, ITT) not vaccinated against COVID-19 or vaccinated before inclusion in the study: ITT_NV_BE. This data set is additional for the analysis of the primary efficiency parameter;
7. Modified population of participants who completed the study according to the protocol (per protocol, PP), not vaccinated against COVID-19 or vaccinated before inclusion in the study: PP_NV_BE. This data set is additional for the analysis of the primary efficiency parameter.

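### The protocol's sample-size section names PP as the primary-analysis population, against the FAS/ITT rule stated everywhere else; that sentence, and the SAP's ITT definition, need correcting

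*Protocol*

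**What the plan says.** **Protocol, Number of participants.** The paragraph that introduces the hypothesis test expects at least 90% of randomised patients to be "suitable for inclusion in the population of the primary analysis (PP"). The same section requires 286 completers per arm (572) and raises this to 315 per arm (630) for 10% premature exclusion and consent withdrawal. The synopsis likewise gives the analysis population as at least 572, not 630.

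**Protocol, Populations for analysis.** The FAS, grouped by intention to treat, "will also be used as the main population to assess performance parameters". PP has a lesser role: "Auxiliary analysis of effectiveness parameters is planned for all subjects who completed the study without significant deviations from the study protocol (PP, Per Protocol").

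**SAP 5.1, Primary Endpoint Analysis.** "The analysis of the primary efficiency parameter will be carried out on the ITT population (main analysis"), with PP as an additional analysis. The secondary endpoints follow the same rule.

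**SAP 5.2.** The size is again a completer count: "number of volunteers who must complete participation in the study in accordance with the protocol is 286 in the group". SAP 5.5 repeats it.

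**SAP 5.5.** ITT is the main data set, and PP serves as a sensitivity check on it. ITT is defined as "all randomized participants who were exposed to the study drug, regardless of the degree of protocol compliance during the study".

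**The concern.** The section that fixes the hypothesis test and the sample size names a different primary population from the sections that fix the analysis.

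The choice matters in this trial because it is open-label with an untreated control, and the protocol's exclusion criteria do not act equally on the two arms:

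- Criteria 5 (intolerance), 7 (contraindication) and 9 (contraception) are limited to the study group.
- Criterion 3 (compliance of 50% or less) uses a scale that counts completed drug cycles, and only Group I has these.
- Criterion 1 applies prohibitions that differ by group. Group I may take no other medication with a possible preventive effect against ARVI, while Group II is barred only from interferon gamma. The same behaviour removes a participant from one arm and not from the other.

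Membership of PP is therefore decided after randomisation, by rules that depend on the arm. Expected events are few: 0.05 × 315 = 15.75 in the control arm and 0.02 × 315 = 6.3 in Group I. A handful of removals in one arm could move the result across the significance threshold. If PP and ITT then disagreed, the sample-size sentence would offer a textual basis for presenting PP as primary.

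**Working it through.** **1. Reproduce the plan's figures.** Inputs from the protocol's Number of participants section: control incidence 5% (the Table 1 row that gives 315), reduction 3 percentage points, t = 1.96, 10% attrition.

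- n = (P1·Q1 + P2·Q2)·t² / (P1 − P2)²
- = (0.05 × 0.95 + 0.02 × 0.98) × 1.96² / 0.03²
- = 0.0671 × 3.8416 / 0.0009 = 286.4 per arm
- 286 × 1.1 = 314.6, rounded to 315 per arm
- 572 / 630 = 90.8%, in line with the 90% expected to qualify for PP

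Both figures reproduce. The size was built on a PP-type completer count.

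**2. Set the role statements side by side.**

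| Place | Primary or main | PP |
|---|---|---|
| Protocol, Number of participants | PP | primary |
| Protocol, Populations for analysis | FAS by intention to treat | auxiliary |
| SAP 5.1, primary endpoint | ITT | additional |
| SAP 5.1, secondary endpoints | ITT | additional |
| SAP 5.5 | ITT | additional, sensitivity |

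One place names PP. All the others name FAS/ITT.

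**3. Power under each population.** Normal approximation with unpooled variance, two-sided 0.05:

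power = Φ( (P1 − P2) / √[(P1·Q1 + P2·Q2)/n] − 1.96 )

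PP-type count, n = 286, 5% vs 2%: standard error 0.01532, ratio 1.959, power 49.9%.

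ITT, n = 315. Let d be the share of Group I at the control risk (assumption). The Group I rate is then (1 − d) × 2% + d × 5%.

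| d | Group I rate | Power at 315 per arm |
|---|---|---|
| 0% | 2.00% | 53.8% |
| 4% | 2.12% | 49.9% |
| 5% | 2.15% | 48.9% |
| 10% | 2.30% | 44.1% |
| 20% | 2.60% | 35.1% |

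The extra ITT participants offset dilution up to about 4%. Beyond that, ITT has less power than 5% vs 2% with 286 per arm. A pooled-variance version gives nearly the same: 49.7% at 286, and 53.5% at 315 with no dilution.

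**4. Where the gap to 80% comes from.** Adding the power term to the protocol's formula gives 0.0671 × (1.96 + 0.84)² / 0.0009 = 585 per arm. The roughly 50% baseline arises because the formula uses 1.96 alone. The population label does not cause it.

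**5. Check the ITT definition.** SAP 5.5 requires exposure to the study drug. Group II is randomised not to use it. Read literally, no control participant who follows the assignment can enter ITT. The definition also differs from the protocol's FAS of all included participants.

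**The case against.** The strongest reply is that there is no real competition between two plans. Every section that assigns analysis roles agrees on FAS/ITT, and against them stands one parenthesis in a sentence about expected evaluability. This stands. A reader might infer that the documents support PP and ITT equally as the primary result, but they do not: the PP label is an outlier. It still needs correcting, because it sits where the protocol says what the sample size is for, and the completer-based sizing in the synopsis and SAP 5.2 follows it.

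A second reply concerns the effect size. A reader might infer that the 3-point reduction is an effect under full adherence, which ITT would dilute. The protocol presents it as a minimal clinically relevant reduction against general-population incidence and does not tie it to adherence. It can serve as an ITT target.

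Third, any single comparison of ITT and PP power is fragile. The protocol's 10% covers premature exclusion and consent withdrawal in both groups, not non-adherence in Group I, and below about 4% dilution ITT has the higher power. That is why the power is given as a range. The figure of 315 also assumes an outcome for every randomised participant, whereas SAP 5.3 analyses available data without imputation. Participants without a day-28 outcome would reduce it.

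**Conclusion.** The inconsistency is real and lies in current text. The documents as a whole point to FAS/ITT, so the sample-size sentence is the one to change. Correction is warranted because exclusions that act only or mainly in Group I leave PP without the protection of randomisation, and because the events are few.

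The effect on power is modest and its direction is not fixed. Against about 50% for 286 per arm, ITT with 315 per arm has about 54% with no dilution, falling to about 35% if 20% of Group I are at control risk. These figures assume 5% vs 2%, two-sided 0.05 and complete outcomes; the dilution shares are not in the documents. The documents do not support attributing the distance from 80% to the population label: most of it comes from the missing power term, which is a separate defect.

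The SAP's ITT definition is part of the same problem. Naming ITT as decisive does not settle the primary population while that definition, read literally, shuts out untreated controls.

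**What to change.** 1. **Protocol, Number of participants.** Rewrite the sentence; do not just swap the label, which would say that 90% of randomised patients enter a set containing all of them. Suggested content: the primary analysis uses FAS/ITT, meaning all randomised participants in their assigned group; only this result decides the primary hypothesis; PP is supportive, and at least 90% of randomised participants are expected to qualify for it.
2. **SAP 5.5.** Remove the drug-exposure condition from the ITT definition, so that it matches the protocol's FAS and can be met by controls. The safety set is defined as identical to the ITT data set, so check that this cross-reference still says what is meant.
3. **Excluded participants.** State that day-28 outcome data already collected on participants excluded under the protocol's exclusion criteria stay in the ITT analysis.
4. **Power.** In the protocol and SAP 5.2, give power for the ITT number and effect as a range over stated dilution assumptions, and deal with the missing power term separately.

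The cost is wording changes in the protocol and the SAP, with no new data collection, and a stated power less favourable than 80%.

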| Sample Size | 630 adult volunteers randomized into 2 parallel groups with a 1:1 distribution, considering a possible 10% premature exclusion and withdrawal of informed consent during the study. The population for analysis will be at least 572 participants: 286 in each group. |

| | |
|------------------------|--|
| Selection criteria | 
Eligible volunteers can participate in the study.
 
Inclusion criteria
 
1. Volunteers of both genders over 18 years old.2. Obtaining a written form of informed consent.3. Ability and consent to participate in this study.4. No symptoms of respiratory infection.5. A negative result of a PCR study for the presence of SARS-CoV-2 RNA according to the biomaterial obtained by nasopharyngeal ¹smear. 
Non-inclusion criteria
 
1. Any other concomitant diseases or conditions that, in the opinion of the research doctor, may distort the results of the study, restrict the rights of the volunteer, or put him at greater risk.2. Contraindications to the use of the study drug.3. Individual intolerance of the ingredients included in the composition of the study drug.4. Pregnancy or breast-feeding.5. Controversial result of PCR test for the presence of SARS-CoV-2 RNA according to the biomaterial obtained by nasopharyngeal smear.6. Participation in a clinical trial using the investigated therapy for 30 days prior to inclusion in this study.7. Disagreement on following reliable contraceptive measures within the study (sexual abstinence; or a combination of 2 different methods: for example, barrier and spermicides, or barrier and intrauterine device, or barrier and hormonal, etc.) – for participants with preserved childbearing potential. |
| Effectiveness criteria | 
Primary effectiveness criteria:
 
The proportion of patients with acute respiratory viral infections, including COVID-19, at the end of the period of preventive administration of the drug (measurement time: 28 days).
 
Secondary effectiveness criteria:
 
1. The proportion of patients with confirmed COVID-19 at the end of the period of preventive treatment of the drug (measurement period: 28 days).2. The proportion of patients with acute respiratory viral |

¹ It is permissible to accept the results of a nasal or pharyngeal smear, as well as the results of studies performed before inclusion in the study for no more than 72 hours.

| | |

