t – critical value of the Student's t-test at the appropriate level of significance.

Considering the ratio of the distribution of patients into groups 1:1 with the above parameters, the study should complete at least 572 patients: 286 in each group. Considering the possible 10% premature exclusion and withdrawal of informed consent, it is necessary to randomize 630 patients (315 in each group).

Below is the dependence of the sample size on the parameters of the magnitude of the expected effect and the minimum difference that needs to be detected (Table 1 – Dependence of the sample size on various parameters).

Thus, the sample size in each group with a random distribution method will be¹⁰:

Table 1 – Dependence of the sample size on various parameters

| The proportion of sick patients in the control group, % | Decreased proportion of cases compared to the control group, % | | | | | | | |
|---|--|-----|-----|-----|-----|----|----|----|
| | 2 | 3 | 4 | 6 | 8 | 10 | 12 | 14 |
| 2 | 207 | - | - | - | - | - | - | - |
| 3 | 411 | 136 | - | - | - | - | - | - |
| 4 | 613 | 227 | 101 | - | - | - | - | - |
| 5 | 809 | 315 | 151 | - | - | - | - | - |
| 6 | 1001 | 400 | 200 | 66 | - | - | - | - |
| 8 | 1373 | 526 | 295 | 109 | 48 | - | - | - |
| 10 | 1728 | 686 | 386 | 151 | 72 | 37 | - | - |
| 12 | 2066 | 840 | 473 | 189 | 95 | 53 | 31 | - |
| 14 | 2387 | 988 | 556 | 228 | 117 | 67 | 41 | 25 |

¹⁰ The calculation is given for a power of 80%, a one-sided significance level of 0.05 and taking into account 10% of the early exclusion of patients from the study

| | | | | | | | | |
|----|------|------|-----|-----|-----|-----|----|----|
| 16 | 2692 | 1126 | 634 | 263 | 136 | 80 | 51 | 33 |
| 18 | 2979 | 1257 | 707 | 297 | 156 | 92 | 59 | 40 |
| 20 | 3249 | 1382 | 777 | 329 | 175 | 106 | 68 | 46 |
| 22 | 3502 | 1498 | 843 | 359 | 193 | 117 | 76 | 53 |
| 24 | 3739 | 1607 | 904 | 387 | 209 | 128 | 84 | 58 |

Thus, in the present study, taking into account the possible 2% exclusion of patients at the screening stage due to non-compliance with the inclusion/non-inclusion criteria, it is planned to include up to 642 volunteers with a 1:1 distribution in each of the 2 parallel groups (study and control), of which up to 321 people will use study drug Ingaron with preventive objective, up to 321 people, will not use the study drug and will form a control comparison group.

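### The 10% loss allowance was added on rather than divided out, so 630 randomised leaves about 567 completers, not 572; and the screening total of 642 is wrongly split into 321 per arm

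*Protocol*

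**What the plan says.** The Sample Size row of the protocol synopsis gives 630 randomised 1:1 with a possible 10% loss, and adds: "The population for analysis will be at least 572 participants: 286 in each group". The Number of participants section repeats 572 (286 per group) as the number who should complete and concludes that "it is necessary to randomize 630 patients (315 in each group"). Earlier in that section the loss is tied to its base: at least 90% of those randomised are expected to qualify for the per-protocol population. The footnote to Table 1 says that its entries already allow for 10% early exclusion.

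After Table 1 the protocol adds 2% for exclusion at screening and reaches up to 642 volunteers. It then allocates all of them 1:1, "of which up to 321 people will use study drug Ingaron with preventive objective", with up to 321 more as controls.

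The SAP uses the same totals with different labels. Section 5.2 states that "number of randomized participants is 315 in a group or total 630 people", and sections 5.2 and 5.5 give 642 as the number screened and 286 per group as the number who must complete in accordance with the protocol.

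**The concern.** Three figures describe one flow of participants, and they do not fit together under the loss rates the plan gives.

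- 572 is worded as a minimum, and 630 is presented as the number that secures it at 10% loss. It does not.
- The protocol rules out replacing excluded participants (Exclusion criteria), and SAP 5.3 rules out imputation, so nothing in the plan makes up the difference.
- People excluded at screening are never allocated, since randomisation takes place at Visit 1. A total that still contains them cannot be divided between the arms. Read literally, the protocol gives two planned arm sizes, 315 and 321, in the same section.

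What is at stake is a set of design figures that a report will be held to. It is not the validity of the comparison.

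**Working it through.** **Inputs (Protocol, Number of participants).** Control incidence 5%; reduction 3 percentage points, so 2% on drug; t = 1.96; 286 per group completing; 10% loss as a share of those randomised; 315 per group randomised; 2% screening exclusion; 642 in total.

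**1. Reproduce the 286.** The printed formula is n = (P1Q1 + P2Q2)t²/(P1 - P2)².
(0.05 x 0.95 + 0.02 x 0.98) x 1.96² / 0.03² = 0.0671 x 3.8416 / 0.0009 = 286.4. This matches 286 per group, 572 in all.

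**2. Reproduce the 315.** 286 x 1.1 = 314.6, rounded up to 315; in total 572 x 1.1 = 629.2, rounded up to 630. The allowance was therefore applied as n x (1 + d).

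**3. Apply the stated loss.** With d a share of those randomised:
- 630 x 0.90 = 567, or 283.5 per group. Shortfall 572 - 567 = 5 (0.9%).
- Number needed for 572: 572/0.90 = 635.6, so 636 (318 per group; 286/0.9 = 317.8).
- Largest loss at which 630 still yields 572: 1 - 572/630 = 9.2%.

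**4. Table 1.** I recomputed all 79 entries as printed formula x 1.1. Of these, 70 agree within 1.5 patients. For example, 4% versus 1% gives 206.2; x 1.1 = 226.8 (printed 227), while /0.9 = 229.1. The other nine all lie in the 3-point column, from a control rate of 8% upward, and fit neither rule (8%: printed 526; 516.9 x 1.1 = 568.6; 516.9/0.9 = 574.3). They do not bear on the chosen size.

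**5. Screening.** 630 x 1.02 = 642.6, printed as 642. Taking 2% off: 642 x 0.98 = 629.2, about 315 per group. An arm size of 321 requires no exclusions at screening.

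**6. Effect on power, 5% versus 2%.** Normal approximation with pooled variance under the null (mean rate 0.035), no continuity correction:
power = Φ{[0.03 - z√(2 x 0.035 x 0.965/n)] / √(0.0671/n)}

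| n per group | one-sided 5% (z = 1.645) | two-sided 5% (z = 1.96) |
|---|---|---|
| 283 | 61.7% | 49.3% |
| 284 | 61.8% | 49.4% |
| 286 | 62.1% | 49.7% |
| 315 | 65.7% | 53.5% |

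Going from 286 to 283-284 costs less than half a point. No row approaches 80%, because the printed formula has no power term, although the z-value for 80% power is listed among the inputs. With that term, the pooled formula needs 463 per group (one-sided) or 588 (two-sided) before any loss.

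**The case against.** The strongest reply is that 572 is not the main analysis set. SAP 5.2 and 5.5 describe it as the number completing in accordance with the protocol. The main efficacy analysis is on the FAS/ITT population in the protocol's Statistical methods and in SAP 5.1 and 5.5, with per-protocol as an addition. This stands. A reader might infer from the shortfall that the primary analysis loses participants or that the trial fails its main objective. The documents do not support that: exclusion or poor compliance removes someone from the per-protocol set, not automatically from ITT. Two qualifications remain. The Number of participants section itself calls per-protocol the primary population, and the synopsis calls 572 the population for analysis without saying which one. Also, with no imputation, some ITT outcomes could still be missing.

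Second, the 10% is only a possible loss, and 572 is kept at 9.2% or below. True, but the plan offers 630 as the number that covers 10%.

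Third, 321 occurs in one sentence, is worded as an upper limit, and the SAP already labels 642 as screened and 630 as randomised; its disposition shell (Table 1 in section 6) also puts screening exclusions before the group split. So a reader should not conclude that 642 will be randomised. The sentence still contradicts the 2% exclusion on which it relies.

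Fourth, 630/0.98 = 642.9 might suggest that the screening figure should be 643. That is rounding on an upper limit and not an error.

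**Conclusion.** The point holds as an inconsistency in the stated numbers. At the plan's own 10% loss, 630 randomised gives about 567 completers (283-284 per group), 5 below the stated minimum, because the allowance was multiplied on instead of divided out. The 321/321 split conflicts with 315 per group in the same section and in the SAP. The consequence is small: about 1% of completers, less than one point of power, and no effect on the ITT set of 630.

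It would be wrong to read the loss allowance as the reason the trial is underpowered. Power of about 62% (one-sided) or 50% (two-sided) at 283-286 per group comes from the missing power term, a separate and much larger defect. Correcting the allowance alone would leave it in place.

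This rests on the 10% being a share of those randomised, which the protocol states, and on 5% versus 2%, the scenario that reproduces 286. The power figures carry no continuity correction. The SAP prescribes the Yates correction when expected frequencies lie between 5 and 10; at 283.5 per group the expected number of cases is 283.5 x 0.035 = 9.9 per group, so it could apply and would lower them. On sidedness the documents disagree: the sample-size text claims "a one-sided level of statistical significance of 5" per cent, while SAP 5.2 says the "statistical criteria used are two-sided due to the lack of a posteriori information".

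**What to change.** Change wording only; no extra participants.

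- In the protocol synopsis (Sample Size), the Number of participants section, and SAP 5.2 and 5.5, give one consistent statement: *up to 642 screened, 630 randomised (315 per group), about 567 (283-284 per group) completing per protocol at 10% loss.* Say that this last figure is the per-protocol target and that the main analysis is ITT.
- Delete the split of 642 into 321 users and 321 non-users.
- Add a note under Table 1 that the allowance was applied as x 1.1 rather than /0.9, and check the nine entries in the 3-point column that follow neither rule.
- Restate power for 5% versus 2% at 283-286 per group as about 62% (one-sided 5%) or about 50% (two-sided 5%, the SAP's test) in place of 80%, and give the missing power term as the reason.

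Raising the total to 636 would restore 572 at 10% loss, but it adds 5 completers to a design that stays near 62% or 50% power. It is not worth doing for this point alone.
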